- 2.1.1.14 Demonstrate adequate organ function as defined in [Table 2](#), all screening labs should be performed within 10 days of treatment initiation.

Table 2 Adequate Organ Function Laboratory Values

System	Laboratory Value
Hematological	
Absolute neutrophil count (ANC)	$\geq 1,000$ /mcL
Platelets	$\geq 100,000$ / mcL
Hemoglobin	≥ 9 g/dL or ≥ 5.6 mmol/L without transfusion or EPO dependency (within 7 days of assessment)
Renal	
Serum creatinine OR Measured or calculated ^a creatinine clearance (GFR can also be used in place of creatinine or CrCl)	≤ 1.5 X upper limit of normal (ULN) OR ≥ 60 mL/min for subject with creatinine levels > 1.5 X institutional ULN
Hepatic	
Serum total bilirubin	≤ 1.5 X ULN OR Direct bilirubin \leq ULN for subjects with total bilirubin levels > 1.5 ULN
AST (SGOT) and ALT (SGPT)	≤ 2.5 X ULN OR ≤ 5 X ULN for subjects with liver metastases
Albumin	≥ 2.5 mg/dL
Coagulation	
International Normalized Ratio (INR) or Prothrombin Time (PT)	≤ 1.5 X ULN unless subject is receiving anticoagulant therapy as long as PT or PTT is within therapeutic range of intended use of anticoagulants
Activated Partial Thromboplastin Time (aPTT)	≤ 1.5 X ULN unless subject is receiving anticoagulant therapy as long as PT or PTT is within therapeutic range of intended use of anticoagulants
^a Creatinine clearance should be calculated per Cockcroft-Gault equation.	

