2.1.2 Exclusion Criteria

- 2.1.2.1 Is currently participating and receiving study therapy or has participated in a study of an investigational agent and received study therapy or used an investigational device within 4 weeks of the first dose of treatment.
- 2.1.2.2 Has a diagnosis of immunodeficiency or is receiving systemic steroid therapy or any other form of immunosuppressive therapy within 7 days prior to the first dose of trial treatment.
- 2.1.2.3 Has a known history of active TB (Bacillus Tuberculosis)

- 2.1.2.4 Hypersensitivity to pembrolizumab or any of its excipients.
- 2.1.2.5 Has had a prior anti-cancer monoclonal antibody (mAb) within 4 weeks prior to study Day 1 or who has not recovered (i.e., \leq Grade 1 or at baseline) from adverse events due to agents administered more than 4 weeks earlier.
- 2.1.2.6 Has had prior targeted small molecule therapy, or radiation therapy within 2 weeks prior to study Day 1 or who has not recovered (i.e., \leq Grade 1 or at baseline) from adverse events due to a previously administered agent.

Note: Subjects with \leq Grade 2 neuropathy are an exception to this criterion and may qualify for the study.

Note: If subject received major surgery, they must have recovered adequately from the toxicity and/or complications from the intervention prior to starting therapy.

- 2.1.2.7 Has active autoimmune disease that has required systemic treatment in the past 2 years (i.e. with use of disease modifying agents, corticosteroids or immunosuppressive drugs). Replacement therapy (e.g., thyroxine, insulin, or physiologic corticosteroid replacement therapy for adrenal or pituitary insufficiency, etc.) is not considered a form of systemic treatment.
- 2.1.2.8 Has known active central nervous system (CNS) metastases and/or carcinomatous meningitis. Subjects with previously treated brain metastases may participate provided they are stable for 6 months (without evidence of progression by imaging for at least four weeks prior to the first dose of trial treatment and any neurologic symptoms have returned to baseline), have no evidence of new or enlarging brain metastases, and are not using steroids for at least 7 days prior to trial treatment. This exception does not include carcinomatous meningitis which is excluded regardless of clinical stability.
- 2.1.2.9 Has history of (non-infectious) pneumonitis that required steroids, evidence of interstitial lung disease or active, non-infectious pneumonitis..

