3.3.1 Dose Modifications

Adverse events (both non-serious and serious) associated with pembrolizumab exposure may represent an immunologic etiology. These adverse events may occur shortly after the first dose or several months after the last dose of treatment. Pembrolizumab must be withheld for drug-related toxicities and severe or life-threatening AEs as per **Table 4** below. See Section 4 for supportive care guidelines, including use of corticosteroids.

Table 4. Dose Modification Guidelines for Drug-Related Adverse Events

Toxicity	Hold Treatment For Grade	Timing for Restarting Treatment	Treatment Discontinuation
Diarrhea/Colitis	2-3	Toxicity resolves to Grade 0-1	Toxicity does not resolve within 12 weeks of last dose or inability to reduce corticosteroid to 10 mg or less of prednisone or equivalent per day within 12 weeks
	4	Permanently discontinue	Permanently discontinue
AST, ALT, or Increased Bilirubin	2	Toxicity resolves to Grade 0-1	Toxicity does not resolve within 12 weeks of last dose
	3-4	Permanently discontinue (see exception below) ^a	Permanently discontinue
Type 1 diabetes mellitus (if new onset) or Hyperglycemia	T1DM or 3-4	Hold pembrolizumab for new onset Type 1 diabetes mellitus or Grade 3-4 hyperglycemia associated with evidence of beta cell failure	Resume pembrolizumab when patients are clinically and metabolically stable
Hypophysitis	2-4	Toxicity resolves to Grade 0-1. Therapy with pembrolizumab can be continued while endocrine replacement therapy is instituted	Toxicity does not resolve within 12 weeks of last dose or inability to reduce corticosteroid to 10 mg or less of prednisone or equivalent per day within 12 weeks

Toxicity	Hold Treatment For Grade	Timing for Restarting Treatment	Treatment Discontinuation
Hyperthyroidism	3	Toxicity resolves to Grade 0-1	Toxicity does not resolve within 12 weeks of last dose or inability to reduce corticosteroid to 10 mg or less of prednisone or equivalent per day within 12 weeks
	4	Permanently discontinue	Permanently discontinue
Hypothyroidism		Therapy with pembrolizumab can be continued while thyroid replacement therapy is instituted	Therapy with pembrolizumab can be continued while thyroid replacement therapy is instituted
Infusion Reaction	2 ^b	Toxicity resolves to Grade 0-1	Permanently discontinue if toxicity develops despite adequate premedication
	3-4	Permanently discontinue	Permanently discontinue

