Pneumonitis	2	Toxicity resolves to Grade 0-1	Toxicity does not resolve within 12 weeks of last dose or inability to reduce corticosteroid to 10 mg or less of prednisone or equivalent per day within 12 weeks
	3-4	Permanently discontinue	Permanently discontinue
Renal Failure or Nephritis	2	Toxicity resolves to Grade 0-1	Toxicity does not resolve within 12 weeks of last dose or inability to reduce corticosteroid to 10 mg or less of prednisone or equivalent per day within 12 weeks
	3-4	Permanently discontinue	Permanently discontinue
All Other Drug-Related Toxicity ^c	3 or Severe	Toxicity resolves to Grade 0-1	Toxicity does not resolve within 12 weeks of last dose or inability to reduce corticosteroid to 10 mg or less of prednisone or equivalent per day within 12 weeks
	4	Permanently discontinue	Permanently discontinue

Note: Permanently discontinue for any severe or Grade 3 drug-related AE that recurs or any life-threatening event.

^a For patients with liver metastasis who begin treatment with Grade 2 AST or ALT, if AST or ALT increases by greater than or equal to 50% relative to baseline and lasts for at least 1 week then patients should be discontinued.

^b If symptoms resolve within one hour of stopping drug infusion, the infusion may be restarted at 50% of the original infusion rate (e.g., from 100 mL/hr to 50 mL/hr). Otherwise dosing will be held until symptoms resolve and the subject should be premedicated for the next scheduled dose; Refer to **Table 5** – Infusion Reaction Treatment Guidelines for further management details.

^c Patients with intolerable or persistent Grade 2 drug-related AE may hold study medication at physician discretion. Permanently discontinue study drug for persistent Grade 2 adverse reactions for which treatment with study drug has been held, that do not recover to Grade 0-1 within 12 weeks of the last dose.

Dosing interruptions are permitted in the case of medical / surgical events or logistical reasons not related to study therapy (e.g., elective surgery, unrelated medical events, patient vacation, and/or holidays). Subjects should be placed back on study therapy within 6 weeks of the

Abbreviated Title: Pembrolizumab in MTC

Version Date: 3/26/18

scheduled interruption. The reason for interruption should be documented in the patient's study record.

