3.5.1 Criteria for removal from protocol therapy

- Completion of protocol therapy
- Clinical progression of disease based on increased symptoms or immune related response criteria (irRC) to also be implemented for disease progression as described in 6.3.2.
- Grade 3 or greater toxicity attributed to treatment that does not resolve to grade 1 within 21 days from time of scheduled treatment.
- Grade 3 or greater autoimmune disease that threatens vital organs.
- Intercurrent illness or medical circumstances. If at any time the constraints of this protocol are detrimental to the patient's health, the patient may be removed from protocol therapy and reasons for withdrawal will be documented.
- Subject decides to withdraw from the study (In this event, the reasons for withdrawal will be documented)
- Investigator discretion
- Positive pregnancy test

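### Liver stopping rules (Table 4, its footnote a, and sections 3.5.1 and 4.1.3) do not fit together for patients who enter with liver metastases and Grade 2 AST/ALT

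*Combined protocol and SAP*

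**What the plan says.** **Entry.** Table 2 (section 2.1.1.14) sets the AST/ALT ceiling at 2.5 x ULN, or "≤ 5 X ULN for subjects with liver metastases".

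**Table 4, liver row, Grade 2.** Hold. Restart when "Toxicity resolves to Grade 0-1". Discontinue when "Toxicity does not resolve within 12 weeks of last dose". Neither cell carries a footnote marker or mentions baseline.

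**Table 4, liver row, Grade 3-4.** The timing cell reads "Permanently discontinue (see exception below" and points to footnote a. The discontinuation cell beside it gives the permanent stop with no marker.

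**Footnote a.** "For patients with liver metastasis who begin treatment with Grade 2 AST or ALT" are to be discontinued if AST or ALT rises by 50% or more over baseline and the rise lasts at least one week.

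**Section 3.5.1.** Remove from therapy for attributed Grade 3 or higher toxicity "that does not resolve to grade 1 within 21 days from time of scheduled treatment". There is no allowance for baseline.

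**Section 4.1.3, hepatic guidance.** For Grade 2 events, liver tests are followed more closely until they are back at baseline values.

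**Scope.** Table 4 is titled "Dose Modification Guidelines for Drug-Related Adverse Events", so an unchanged entry value triggers nothing.

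**The concern.** Most of these rules are written in absolute grades. That works for a patient who starts at Grade 0. It does not work for one who starts at Grade 2, and the protocol knowingly enrols such patients. For them a grade-based recovery target, a baseline-relative trigger and a baseline-relative monitoring end point apply together, and nothing says which takes precedence.

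The stake is consistent handling of liver events. Depending on the cell read, the same patient could be held, stopped or left on treatment. The error can go either way: removing a patient who has returned to the entry value, or continuing one whom another cell stops.

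**Working it through.** The plan gives no figure to reproduce. The check sets the rules side by side and adds simple arithmetic.

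**Inputs.** From the documents: entry ceiling 5 x ULN with liver metastases (Table 2); footnote trigger 1.5 x baseline, sustained for one week; the Grade 2 row's hold, Grade 0-1 restart and 12-week limit; the 21-day limit in section 3.5.1. Assumed: Grade 2 begins above L x ULN, with L between 2.5 and 3.0, and Grade 3 begins above 5 x ULN. Section 6.4 adopts CTCAE 4.0 but prints no cut-offs.

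**1. Restart target against entry value.** This step needs no cut-off, because Grade 0-1 lies below Grade 2 by definition. A patient enters at Grade 2, has a drug-related rise within Grade 2, is held, and returns to the entry value. Read literally, the restart condition is not met and the 12-week discontinuation rule follows. By the monitoring end point in section 4.1.3, the same patient has recovered. For scale, the fall below baseline needed to restart is 1 - L/b for a baseline of b x ULN. At b = 4.0 this is 1 - 3.0/4.0 = 25% with L = 3.0, or 1 - 2.5/4.0 = 37.5% with L = 2.5.

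**2. Footnote trigger within Grade 2.** The trigger is 1.5b and stays within Grade 2 while 1.5b ≤ 5, that is b ≤ 5/1.5 = 3.33 x ULN. At b = 3.1 it is 4.65 x ULN, still Grade 2: footnote a discontinues, while the Grade 2 row holds and allows up to 12 weeks. The share of the Grade 2 baseline range in which this can happen is (3.33 - L)/(5 - L):
- L = 3.0: 0.33/2.0 = 0.17, about one sixth.
- L = 2.5: 0.83/2.5 = 0.33, about one third.

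These are shares of the range of values, not of patients.

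**3. Grade 3 reached before the footnote trigger.** Above 3.33 x ULN, Grade 3 comes first. The rise needed to reach it is 5/b - 1.

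| Baseline (x ULN) | Rise to Grade 3 | Footnote trigger (x ULN) |
|---|---|---|
| 3.1 | 61% | 4.65 (Grade 2) |
| 4.0 | 25% | 6.0 |
| 4.5 | 11% | 6.75 |

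Take b = 4.0 and a drug-related peak of 5.5 x ULN, a rise of 5.5/4.0 - 1 = 37.5%. The timing cell sends the reader to footnote a, whose trigger is not met. The footnote does not say whether to hold or continue, and it is equally silent on a larger rise lasting under a week. The adjacent discontinuation cell says stop. If the patient stays on and returns to 4.0 x ULN, the value is still Grade 2, so the requirement in section 3.5.1 to reach grade 1 within 21 days is not met.

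**The case against.** The strongest reply is that footnote a is a signposted exception. The Grade 3-4 row names it, and a general rule with a stated exception is not a contradiction. That stands: a reader might infer that the row and the footnote give opposite orders, and at Grade 3-4 the text does not support that. The missing marker in the neighbouring cell could be a typographical slip. What the reply leaves open is the Grade 2 row, which has no marker; the footnote's silence on smaller or shorter Grade 3 rises; and section 3.5.1, which makes no reference to the footnote.

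A second reply is that the toxicity to be resolved is only the drug-related increment, so a return to baseline counts, as section 4.1.3 suggests. Table 4 is indeed limited to drug-related events, so it would be wrong to infer that every patient entering at Grade 2 must be stopped. The problem arises only after a hold for a drug-related rise, and only on the literal reading. But the restart cell names a grade as its end point, so the literal reading is the natural one.

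A third reply is that footnote a names its own population and is not limited by its text to Grade 3, so it could be taken as the specific rule throughout. That is possible, but its only marker is in the Grade 3-4 row, so the reader has to guess.

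**Conclusion.** The point holds as an inconsistency among stated stopping rules for one defined subgroup. The restart problem follows from the text alone, read literally. The overlap within Grade 2 rests on the assumed cut-offs and covers one sixth to one third of the Grade 2 baseline range.

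The number of patients affected cannot be derived: the documents do not say how many will enter with liver metastases and Grade 2 AST/ALT. It is probably small, because a patient must both enter in that state and then have a drug-related liver event. Section 11.1.2 reports immune-mediated hepatitis in 16 of 1567 patients (1%). That is narrower than all drug-related AST/ALT rises and may not fit patients with raised baselines, so it is only a rough indication.

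Three further inferences are not supported:
- **Chance of a conflict.** A reader might apply an assumed prevalence of Grade 2 entry to the 30 planned patients. That counts entrants, not conflicts, and the documents give no prevalence.
- **Primary endpoint.** A reader might infer damage to the response analysis. Removal from therapy (section 3.5.1) is separate from going off study (section 3.5.2), whose list does not include toxicity, and scans continue while patients remain on study. No effect on the rule of 4 responders in 15 is shown.
- **Neuropathy.** Section 2.1.2.6 says subjects with up to "Grade 2 neuropathy are an exception to this criterion and may qualify for the study". The matching Table 4 row holds only from Grade 3, Grade 2 holds are discretionary under footnote c, and section 3.5.1 starts at Grade 3. The liver argument does not carry over in the same form.

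**What to change.** The sponsor and investigator should reconcile Table 4's liver rows, footnote a, section 3.5.1 and section 4.1.3 for patients with liver metastases who start at Grade 2 AST/ALT. The revised text should state:

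- whether footnote a governs the Grade 2 row, the Grade 3-4 row or both, and whether it applies to the timing and discontinuation cells alike;
- what happens at Grade 3 when the rise is below 50% or lasts less than a week;
- whether recovery is judged against grade or against the patient's baseline, in the same terms in Table 4 and section 3.5.1.

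Which rule is right is a clinical decision, and no view is taken on it here. The cost is a wording amendment to Table 4 and the two sections. Sample size, visit schedule and analysis do not change.

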3.3.2 Dosing Delay

Dosing delay is permitted by 7 days before or after scheduled treatment for logistical purposes (given travel requirements of our patients). If there are changes in the schedule, the subsequent dose may not be given less than 18 days later.

3.4 Study Calendar

Procedure	Screening/ Baseline ⁵	Treatment Cycles (21 days +/- 7 days) ¹								Cycle 9 and beyond	Post Treatment ⁶	
		C1 D1	C2 D1	C3 D1	C4 D1	C5 D1	C6 D1	C7 D1	C8 D1			
History and PE	X ²	X	X	X	X	X	X	X	X	X	X	X
Vital signs	X ²	X	X	X	X	X	X	X	X	X	X	X
Performance Score	X ²											
Height/Weight	X ³											
HIV, Hep B, C	X											
Pregnancy Test (Urine or Serum beta-HCG)	X ²											
UA ⁴	X ²											
PT/INR and PTT	X ²											
Chemistries ⁷	X ²	X	X	X	X	X	X	X	X	X	X	X
CBC	X ²	X	X	X	X	X	X	X	X	X	X	X
TSH	X ²			X	X	X	X	X	X	X	X	X
T/B/NK subsets	X ²	X	X	X	X	X	X	X	X	X	X	X
Tumor Markers: Calcitonin and CEA	X ²	X	X	X	X	X	X	X	X	X	X	X
Correlative Research Studies (research bloods see Appendix B)	X	continue at 3 month intervals									X ⁸	
Radiological Assessments (MRI or CT Neck, Ch/Abd/Pelvis, Bone Scan) ³	X	continue at 3 month intervals										
EKG ³	X	continue at 3 month intervals									X	
Biopsy (optional) ⁸												
Adverse Events		X										
Concomitant Medications		X										

¹ If patient is delayed, subsequent infusion must be at least 18 days later

Abbreviated Title: Pembrolizumab in MTC

Version Date: 3/26/18

² Must be done within 10 days prior to initiation of study therapy

³ Must be done within 8 weeks prior to initiation of study therapy, and then will be done every 3 months while patients remain on study

⁴ May be omitted if patient is incontinent and cannot provide a urine sample

⁵ Baseline/Screening requirements may also be used for Day 1 requirements if logistically necessary

⁶ Post-Therapy Assessment done 3 weeks after last treatment when logistically feasible (with a possible extension to 4 weeks if logistically necessary). Patients will be offered enrollment in the 04-C-0274 "Follow-Up Study of Subjects Previously Enrolled in Immunotherapy Studies Utilizing Gene Transfer or other Immunotherapeutic Agents" once off study.

⁷ Chemistries: sodium, potassium, chloride, CO₂, creatinine, glucose, BUN, albumin, calcium, magnesium, phosphorus, alkaline phosphatase, ALT, AST, total bilirubin, direct bilirubin, LD, total protein, total CK, uric acid

⁸ When logistically feasible, pre-treatment and post-treatment samples may be obtained from consenting patients.

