2 ELIGIBILITY ASSESSMENT AND ENROLLMENT

2.1 Eligibility Criteria

2.1.1 Inclusion Criteria

- 2.1.1.1 Diagnosis: Patients must have histologically confirmed medullary thyroid cancer by the Laboratory of Pathology or a pathology report and history consistent with medullary thyroid cancer. It is not uncommon for a secondary, minor pathologic focus of another form of thyroid cancer to be coincidentally found in 15-20% of patients with medullary thyroid cancer²¹. In such cases, eligibility is based on the discretion of the investigator.
- 2.1.1.2 Patients must have evidence of metastatic medullary thyroid cancer including disease that is evaluable on bone, CT scan or MRI. (Patients who are surgical candidates and potentially rendered disease free with surgical resection are not eligible.)
- 2.1.1.3 Patients must have elevated calcitonin levels greater than 40 pg/mL
- 2.1.1.4 Patients must have minimal or no disease related-symptoms (Minimal symptoms will include those that do not affect activities of daily living or pain that does not require regularly scheduled narcotics.)
- 2.1.1.5 Patients must have evaluable disease on imaging
- 2.1.1.6 No history of seizures, encephalitis, or multiple sclerosis.
- 2.1.1.7 Age \geq 18 years
- 2.1.1.8 ECOG performance status of 0-1 at study entry (Karnofsky \geq 70) (See [Appendix A](#)).
- 2.1.1.9 Female subject of childbearing potential should have a negative urine or serum pregnancy within 72 hours prior to receiving the first dose of study medication. If the urine test is positive or cannot be confirmed as negative, a serum pregnancy test will be required.
- 2.1.1.10 Female subjects of childbearing potential must be willing to use an adequate method of contraception as outlined in Section [10.6](#), Contraception, for the course of the study through 120 days after the last dose of study medication.
Note: Abstinence is acceptable if this is the usual lifestyle and preferred contraception for the subject
- 2.1.1.11 Male subjects of childbearing potential must agree to use an adequate method of contraception as outlined in Section [10.6](#), Contraception, starting with the first dose of study therapy through 120 days after the last dose of study therapy.
Note: Abstinence is acceptable if this is the usual lifestyle and preferred contraception for the subject
- 2.1.1.12 Willing to travel to the NIH for follow-up visits
- 2.1.1.13 Able to understand and sign informed consent.

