2.3.3.2 Laboratory studies

- Complete blood count plus differential and platelet count
- Chemistries (sodium, potassium, chloride, CO₂, creatinine, glucose, BUN, albumin, calcium, magnesium, phosphorus, alk phos, ALT, AST, total bilirubin, direct bilirubin, LD, total protein, total CK and uric acid)
- PT, PTT
- Urinalysis (may be omitted if patient is incontinent and cannot provide a urine sample)
- Serum calcitonin and CEA
- TSH
- Urine Beta-HCG for women of child-bearing age (repeated within 48 hours prior to treatment). (Serum Beta-HCG may be done if urine is positive or inconclusive).

Females of childbearing potential (FCBP): A female of childbearing potential is a sexually mature woman who:

- a) Has not undergone a hysterectomy or bilateral oophorectomy
- b) Has not been naturally postmenopausal for at least 24 consecutive months (i.e. has had menses at any time in the preceding 24 consecutive months).
- c) Has a congenital or acquired condition that prevents childbearing

In addition, patients, both male and female, should be willing to practice effective birth control during the study and for four months following the last study treatment, unless they have had a prior hysterectomy, bilateral oophorectomy, congenital conditions associated with infertility or azoospermia.

2.4 Treatment Assignment and Randomization/Stratification Procedures:

Cohorts

Number	Name	Description
1	First cohort	Patients with prior vaccine therapy
2	Second cohort	Patients without prior vaccine therapy

Arms

Number	Name	Description
1	Pembrolizumab	Pembrolizumab treatment for 2 years at Q3W

Randomization and Arm Assignment

Patients will be enrolled to Cohort 1 (previous vaccine) or Cohort 2 (no previous vaccine) based on their treatment history. This will be established at each patients' screening visit and noted on the eligibility criteria. Patients in cohort 1 and cohort 2 will be directly assigned to Arm 1.

[figure not shown]

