3 STUDY IMPLEMENTATION

3.1 Study Design

This will be an open label study in which all patients receive pembrolizumab. Patients will be assigned to specific cohorts based on their previous treatment with an immune stimulating therapeutic cancer vaccine.

Treatment Duration with Pembrolizumab: 2 years (at 3 week intervals)

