7.3.3 Reporting of Pregnancy and Lactation

Although pregnancy and lactation are not considered adverse events, it is the responsibility of investigators or their designees to report any pregnancy or lactation in a subject (spontaneously reported to them) that occurs during the trial.

Pregnancies and lactations that occur after the consent form is signed but before treatment allocation/randomization must be reported by the investigator if they cause the subject to be excluded from the trial, or are the result of a protocol-specified intervention, including but not limited to washout or discontinuation of usual therapy, diet, placebo treatment or a procedure.

Pregnancies and lactations that occur from the time of treatment allocation/randomization through 120 days following cessation of manufacturer's product, or 30 days following cessation of treatment if the subject initiates new anticancer therapy, whichever is earlier, must be reported by the investigator. All reported pregnancies must be followed to the completion/termination of

the pregnancy. Pregnancy outcomes of spontaneous abortion, missed abortion, benign hydatidiform mole, blighted ovum, fetal death, intrauterine death, miscarriage and stillbirth must be reported as serious events (Important Medical Events). If the pregnancy continues to term, the outcome (health of infant) must also be reported.

Such events must be reported within 2 working days of receipt to Merck Global Safety. (Attn: Worldwide Product Safety; [contact]).

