10.8 Use In Pregnancy

If a subject inadvertently becomes pregnant while on treatment with pembrolizumab, the subject will immediately be removed from the study. The site will contact the subject at least monthly and document the subject's status until the pregnancy has been completed or terminated. The outcome of the pregnancy will be reported to the study PI and to Merck without delay and within 24 hours to the study PI and within 2 working days to Merck if the outcome is a serious adverse experience (e.g., death, abortion, congenital anomaly, or other disabling or life-threatening complication to the mother or newborn).

The study PI will make every effort to obtain permission to follow the outcome of the pregnancy and the condition of the fetus or newborn. If a male subject impregnates his female partner the study personnel at the site must be informed immediately and the pregnancy reported to the study PI and to Merck and followed as described above and in Section 7.3.3.

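### A positive pregnancy test is a ground for removal from therapy, but no pregnancy test is scheduled after the first dose

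*Combined protocol and SAP*

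**What the plan says.** **Removal rules.** Section 3.5.1 includes "Positive pregnancy test" in its list of reasons to come off protocol therapy. Section 10.8 adds: "If a subject inadvertently becomes pregnant while on treatment with pembrolizumab, the subject will immediately be removed from the study".

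**Scheduled testing.** The section 3.4 calendar has a row "Pregnancy Test (Urine or Serum beta-HCG" with a single mark, under Screening/Baseline. Its footnote reads "Must be done within 10 days prior to initiation of study therapy". Section 2.3.3.2, which lists screening laboratory work, asks for "Urine Beta-HCG for women of child-bearing age (repeated within 48 hours prior to treatment". Section 2.1.1 requires a negative result "within 72 hours prior to receiving the first dose of study medication".

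**Reporting.** Section 7.3.3 makes investigators responsible to "report any pregnancy or lactation in a subject (spontaneously reported to them) that occurs during the trial".

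**Exposure.** Section 3.1 gives "Treatment Duration with Pembrolizumab: 2 years (at 3 week intervals". Section 11.1.2 states that the drug can harm a fetus. Section 10.7 requires abstinence or listed contraception until 120 days after the last dose.

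**The concern.** A stopping rule defined by a laboratory result normally has that result collected on a schedule. Here every scheduled pregnancy test falls before the first dose, while the rule is meant to act during the treatment that follows. Section 3.3 says each dose is given after the calendar's procedures are complete, so a site that follows the calendar exactly will keep dosing a woman of childbearing potential without ever producing the result that section 3.5.1 refers to.

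What is at stake is patient and fetal safety: how soon a pregnancy is recognised while a drug the protocol describes as potentially harmful to the fetus is given every three weeks. No efficacy inference is at stake.

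**Working it through.** **1. Places where a pregnancy test is called for**

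| Source | Timing | Relation to first dose |
|---|---|---|
| 3.4 calendar, footnote 2 | within 10 days before therapy starts | before |
| 2.3.3.2 screening laboratory list | repeat within 48 hours before treatment | before |
| 2.1.1 inclusion criterion | negative within 72 hours before first dose | before |
| 3.4 calendar, Cycles 1 to 8, and Cycle 9 and beyond | no mark | none |
| 3.4 calendar, Post Treatment | no mark | none |

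Scheduled tests after the first dose: 0.

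**2. Is the gap an artefact of a broken table?** Unlikely. In the same calendar, the rows for chemistries, blood count and tumour markers keep their marks across the cycles and the post-treatment column. The footnotes also differ. Footnote 3 (imaging, EKG) adds a repeat every 3 months on study, while footnote 2 (pregnancy test) adds none. The calendar states on-treatment repeats where it intends them.

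**3. Could the 48-hour repeat mean before every dose?** The item sits under the tests due within 10 days before therapy starts, so the natural reading is before the first dose.

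**4. Doses covered by the gap.** The documents give no dose count, so there is no stated figure to reproduce. Inputs are 2 years (730 days) and a 21-day interval.

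- Doses = floor(730 / 21) + 1 = floor(34.8) + 1 = 35. Using 728 or 731 days also gives 35.
- If every interval were 28 days, the upper end of the calendar's 7-day window: floor(730 / 28) + 1 = 26 + 1 = 27.
- If every interval were 18 days, the minimum gap in section 3.3.2: floor(730 / 18) + 1 = 40 + 1 = 41.

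So there are about 35 doses on schedule, with outer bounds of 27 to 41, for a patient who completes two years. A patient who stops early receives fewer.

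**5. Doses given before recognition.** The documents give no figure for this delay. If a pregnancy went unnoticed for 6 to 12 weeks (an assumption), 6 / 3 = 2 to 12 / 3 = 4 further doses would fall in that time.

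**6. After the last dose.** The post-therapy visit is at 3 weeks, or 4 if needed (21 to 28 days). Contraception runs to day 120. Days after that visit: 120 − 28 = 92 to 120 − 21 = 99. A test at that visit would leave 92 to 99 days uncovered.

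**The case against.** The best defence is that a removal rule need not have a routine test behind it. Section 3.5.1 does not say that the positive test must be a scheduled one, section 10.8 names no test at all, and other grounds in 3.5.1, such as intercurrent illness, are also event-driven. The risk is also controlled in advance: section 2.1.2 excludes anyone expecting to conceive through 120 days after the last dose, and section 10.7 bars entry if reliable contraception is in doubt. The affected group may be small, since section 1.2 puts typical presentation in the fifth or sixth decade.

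Much of this stands, and it rules out several stronger readings that a reader might infer:

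- *That the rule can never act on treatment.* An unscheduled positive test triggers 3.5.1, and 10.8 applies however the pregnancy is found.
- *That only the patient's own report can reveal a pregnancy.* History and physical examination are scheduled at every cycle, and abdomen and pelvis imaging every 3 months. Neither is a pregnancy test, but either could bring one to light. Section 7.3.3 concerns what investigators must report; it does not set the means of detection.
- *That a single test precedes the first dose.* The 48-hour repeat in 2.3.3.2 adds a second.
- *That the safety objective will undercount exposed pregnancies.* Section 7.3.3 says pregnancy is not considered an adverse event, and section 1.1.2 sets no pregnancy count. An undercount is not shown.

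The defence does not supply a scheduled trigger. Imaging 3 months apart fits poorly with a requirement for immediate removal. The protocol also nowhere says that testing on treatment is to be done for cause, so the reader cannot tell whether the blank cells are a choice or an omission.

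**Conclusion.** The point holds as a gap in safety monitoring. The protocol has a removal criterion defined by a test, and no such test is scheduled after the first dose, across about 35 doses for a patient who completes two years, or at the post-treatment visit. The conclusion rests on reading the 48-hour repeat as a pre-first-dose test and on taking the calendar marks as printed; the layout supports both.

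The practical size cannot be fixed from the documents. The number of women of childbearing potential is not given, although enrolment from age 18 and the provisions for this group show that they are expected. The 2 to 4 doses before recognition depend entirely on the assumed delay. Sample size, response rule and error rates are untouched. The matter should be corrected, but it does not threaten the trial's conclusions.

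**What to change.** Reconcile sections 2.1.1, 2.3.3.2, 3.4, 3.5.1, 7.3.3 and 10.8 so that the removal criterion has a scheduled trigger. The direct way is to enter the pregnancy test for women of childbearing potential in the calendar's on-treatment and post-treatment columns, at a frequency the sponsor sets. The same amendment should bring the three pre-treatment timings (10 days, 48 hours, 72 hours) into one consistent statement. Which timing or frequency applies is for the sponsor to decide.

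The cost is a calendar entry and an inexpensive laboratory test. The calendar already accepts serum beta-HCG, and blood for chemistries is drawn at every cycle and post-treatment, so those columns need no extra visit or draw. The test would apply to a subset of a trial capped at 32 patients. One limitation remains: the post-treatment visit falls 3 to 4 weeks after the last dose, so a test there does not cover the full 120-day contraception period, and the protocol should say how the rest is handled.
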